16.0 Health Information and Privacy Compliance

16.1 Select which of the following is applicable to your research:

- My research does not require access to individual health information and therefore assert HIPAA does not apply.
- I am requesting that all research participants sign a HIPCO approved HIPAA Disclosure Authorization to participate in the research (either the standalone form or the combined consent and HIPAA Authorization).
- I am requesting the IRB to approve a Waiver or an alteration of research participant authorization to participate in the research.

Appropriate Use for Research: N/A

- An external IRB (e.g. Advarra) is reviewing and we are requesting use of the authorization language embedded in the template consent form in lieu of the U of M stand-alone HIPAA Authorization. Note: External IRB must be serving as the privacy board for this option.

16.2 Identify the source of Private Health Information you will be using for your research (Check all that apply)

- I will use the Informatics Consulting Services (ICS) available through CTSI (also referred to as the University's Information Exchange (IE) or data shelter) to pull records for me
- I will collect information directly from research participants.
- I will use University services to access and retrieve records from the Bone Marrow Transplant (BMPT) database, also known as the HSCT (Hematopoietic Stem Cell Transplant) database.
- I will pull records directly from EPIC.
- I will retrieve record directly from axiUm / MiPACS
- I will receive data from the Center for Medicare/Medicaid Services
- I will receive a limited data set from another institution
- Other. Describe:

16.3 Explain how you will ensure that only records of patients who have agreed to have their information used for research will be reviewed.

Patients on the surgery schedule for renal transplants will be screened before being approached by research to ensure that they have not opted-out of

MEDICAL PROTOCOL (HRP-590)

PROTOCOL TITLE: Comparison of normothermia maintenance between resistive blanket and forced air warming systems in renal transplant surgery

VERSION DATE: V43 January June 6, 2022

research and meet criteria for approaching. For data collection, research staff will only be accessing records of patient's with a signed consent. Participants who have withdrawn from the study will not be included.

16.4 Approximate number of records required for review: 200

16.5 Please describe how you will communicate with research participants during the course of this research. Check all applicable boxes

- This research involves record review only. There will be no communication with research participants.
- Communication with research participants will take place in the course of treatment, through MyChart, or other similar forms of communication used with patients receiving treatment (consent and assignment to one of two warming methods)
- Communication with research participants will take place outside of treatment settings. If this box is selected, please describe the type of communication and how it will be received by participants.

16.6 Explain how the research team has legitimate access to patients/potential participants:

Study staff approaching participants are part of the surgical team (anesthesiology). All study staff involved in this study have successfully completed all regulatory requirements (HIPPA, CITI, GCP, Fairview requirements). Privacy is taken very seriously and only consented patients will be accessed.

16.7 Location(s) of storage, sharing and analysis of research data, including any links to research data (check all that apply).

- In the data shelter of the [Information Exchange \(IE\)](#)
 - Store Analyze Share
- In the Bone Marrow Transplant (BMT) database, also known as the HSCT (Hematopoietic Stem Cell Transplant) Database
 - Store Analyze Share
- In REDCap (recap.ahc.umn.edu)
 - Store Analyze Share
- In Qualtrics (qualtrics.umn.edu)
 - Store Analyze Share
- In OnCore (oncore.umn.edu)

MEDICAL PROTOCOL (HRP-590)

PROTOCOL TITLE: Comparison of normothermia maintenance between resistive blanket and forced air warming systems in renal transplant surgery

VERSION DATE: V43 January June 6, 2022

Store Analyze Share

In the University's Box Secure Storage (box.umn.edu)

Store Analyze Share

In an AHC-IS supported server. Provide folder path, location of server and IT Support Contact:

Store Analyze Share

In an AHC-IS supported desktop or laptop.

Provide UMN device numbers of all devices:

Store Analyze Share

Other. Describe:

Indicate if data will be collected, downloaded, accessed, shared or stored using a server, desktop, laptop, external drive or mobile device (including a tablet computer such as an iPad or a smartform (iPhone or Android devices) that you have not already identified in the preceding questions

I will use a server not previously listed to collect/download research data

I will use a desktop or laptop not previously listed

I will use an external hard drive or USB drive ("flash" or "thumb" drives) not previously listed

I will use a mobile device such as a tablet or smartphone not previously listed

16.8 Consultants. Vendors. Third Parties: Data will not be shared with the company supplying the product.

16.9 Links to identifiable data: N/A

16.10 Sharing of Data with Research Team Members: Team members will use box to share data. No email or other systems will be used.

16.11 Storage and Disposal of Paper Documents: Signed paper consents will be securely stored in a regulatory binder for 5 years.

17.0 Confidentiality

17.1 Data Security:

Only the core study team (PI, co-PI, and support personnel) will have access to PHI and data during the initial collection process. Intraoperative recording of relevant events for the study will be recorded on paper or in REDCap on an IPAD in the operating room, which will be imported into REDCap and saved in box in a way that de-identifies the data. Intraoperative subject vitals will also be exported

MEDICAL PROTOCOL (HRP-590)

PROTOCOL TITLE: Comparison of normothermia maintenance between resistive blanket and forced air warming systems in renal transplant surgery

VERSION DATE: V43 January June 6, 2022

from EPIC into spreadsheet format and be saved on research computers in a de-identified fashion. Data collected by the VitalIDB software package will be done in real-time to a hospital-owned computer for use dedicated to the research team, and will have no patient identifiers except for date and time of the data collected, and subject number, and will be merged into the spreadsheet containing the data imported from EPIC. Data will then be processed on these computers that are dedicated solely to the research team. A separate spreadsheet of PHI (patient name, MRN, date of surgery, procedure) will be compiled of study subjects in the case additional information needs to be collected or verified. The spreadsheet with PHI and data spreadsheets will be saved in an encrypted format in BOX. All computers that are dedicated to the research team will not leave the research site (Fairview hospitals, University of Minnesota) and be secured in a locked office when not in use. Transmission of data will be performed within approved University storage and transfer modalities (encrypted e-mail, local network drives, etc.). Original consent documents and data collected on paper, which will include patient information, will be stored in a locked cabinet in a locked research office, accessible only to the core study team.

18.0 Provisions to Monitor the Data to Ensure the Safety of Participants

18.1 Data Integrity Monitoring:

A detailed review of all participants and participant data will be conduct at monthly intervals by the PI or co-PI to ensure data is being recorded and analyzed appropriately. Any missing data or abnormal data findings will trigger a detailed review of raw data from EPIC and measures will be taken to train the staff to minimize the chance for recurrence and to improve the process of data collection and analysis. The PI or co-PI will also review EPIC records of each subject to verify protocols were followed and to note if any adverse events occur, and if any rescue interventions were implemented and implemented correctly.

Any adverse events, whether related to the study or not with regards to temperature management, will be reported to the study team in addition to chart review. An adverse event log will be maintained, with events reported to the IRB. If there is any question as to whether the event was related to the study, the case will be referred to [name], the Department of Anesthesiology's Vice Chair for Research and the Departments Quality Assurance Event monitor, for review and adjudication. [name] will be empowered to temporarily halt enrollment if any safety concerns are noted - although the final decision regarding halting or resuming the study will be referred to the Department of Anesthesiology's DSMB (see below for details).

18.2 Data Safety Monitoring:

The Department of Anesthesiology has a designated "DSMB" headed by [name] and including Drs. [name] and [name]. Given the low risk

MEDICAL PROTOCOL (HRP-590)

PROTOCOL TITLE: Comparison of normothermia maintenance between resistive blanket and forced air warming systems in renal transplant surgery

VERSION DATE: V43 January June 6, 2022

nature of this study, our plan is for the DSMB to receive blinded (A vs B) data after the completion of the 55th patient (the halfway point). While statistical stopping rules for non-inferiority studies remain uncertain, we will use a well-established O'Brien-Fleming procedure and will stop the study if the SUPERIORITY of either method is established, based on an intergroup Z-score difference of 2.78.

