Patient core temperature will be measured with a nasopharyngeal temperature probe. The patient's temperature will be monitored and recorded for the duration of surgery with the selected warming system. Vital signs, including continuous blood pressure, heart rate, oxygen saturation, and end-tidal carbon dioxide, will be monitored and recorded in Epic as is routine with all anesthetics performed. Our primary outcome variable is the NP temperature as recorded at the end of the surgery.

After the surgery, the patient will be transported to the PACU in a timely fashion. Temperature measurement in the PACU will be standardized with skin temperature probes (3M Spot-On) that will be placed on the forehead prior to leaving the operating room. If there is an unexpected delay in transporting the patient to the PACU, that will be documented and the temperature upon arrival to PACU will not be valid.

Data to be collected about participants and the source records that will be used to collect those data:

From Epic:

- Age
- Sex
- MRN
- Height
- Weight
- BMI
- Date of procedure
- Procedure performed

MEDICAL PROTOCOL (HRP-590)

PROTOCOL TITLE: Comparison of normothermia maintenance between resistive blanket and forced air warming systems in renal transplant surgery

VERSION DATE: V43 January June 6, 2022

- Nasopharyngeal temperature throughout surgery (every minute)
- Time at warming system being switched (resistive blanket or forced air)
- Time when patient reaches 37°C
- Time at OR departure
- Time sign-out from PACU prior to transfer to regular nursing floor
- Blood product volume administered to patient (red blood cells, fresh frozen plasma, platelets, and cryoprecipitate)
- Recorded incidence of rescue warming used for when patient's temperature is at 35.5°C (requiring rescue means the need to turn on the additional forced air warming device that may be due to severe hypothermia and uncontrolled bleeding)

Individually Identifiable Health Information: See above

HIPAA Agreement: Attached

5.3 Study Duration:

Individual Subject Participation Duration: Patients will be in the study for their scheduled procedure and for 1 hour following their procedure. Duration of the surgical procedure, is typically 2-5 hours depending on the surgery required. Following the study, participants will not be approached at any time, for any reason as it pertains to their study participation.

Total Study Duration (all Participants): approximately 1 year

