10.0 Local Number of Participants

10.1 Local Number of Participants to be Consented: 130

10.2 Basis for Sample Size Calculation:

The sample size of 98 total patients was calculated in consultation with a statistician on the assumption that there would be a significant mean difference of 0.5°C (SD=0.75) (see Section 15.2 for more details). To account for an 80% enrollment rate, we estimate we will need to approach 123 patients for the study.

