15.0 Statistical Considerations

15.1 Data Analysis Plan:

1. Our primary outcome variable is the patient's temperature at the end of surgery.

2. Secondary outcome variables also include:

- AUC of time versus temperature curves;
- temperatures at set points during operative period;
- blood loss volumes

All continuous measures will be summarized with mean (standard deviation) or median (interquartile range) based upon evaluation of normality using statistical tests (e.g., Shapiro-Wilk) and graphical representation (e.g., histograms, boxplots). Categorical measures will be summarized by count (percent).

The secondary outcomes are continuous measures and will be compared using two-sided two-sample t-tests for unadjusted comparisons of the groups. Adjusted comparisons will use linear regression models to account for potential confounders that may affect the outcome based upon the clinical literature.

Safety outcomes of interest include the incidence of hyperthermia, rescue warming, and incidence of thermal injury. These are categorical variables and will be compared using the χ^2 test or Fischer's exact test for unadjusted comparisons and with logistic regression models to account for potential confounders.

Final data set will be assessed for missing data, depending on rate of missing data, we will use statistical methods to account for missing data

15.2 Power Analysis:

A mean difference of 0.5°C in patient temperatures between the two devices would be clinically meaningful. However, limited data exists, so a range of standard deviations were explored to examine the different sample sizes needed at 80% and 90% power (assuming a two-sided two-sample t-test with $\alpha=0.05$).

Power	SD	N per Group	Overall N
0.8	0.25	6	12

MEDICAL PROTOCOL (HRP-590)

PROTOCOL TITLE: Comparison of normothermia maintenance between resistive blanket and forced air warming systems in renal transplant surgery

VERSION DATE: V43 January June 6, 2022

	0.5	17	34
	0.75	37	74
	1	64	128
0.9	0.25	7	14
	0.5	23	46
	0.75	49	98
	1	86	172

We will take a conservative approach by enrolling 49 patients per group (98 patients total). As this is a minimal risk study, we expect to an 80% enrollment rate; we will approach (98 + 20% = 123 patients). In 2019, the University of Minnesota Medical Canter performed approximately 240 renal transplants for a total of ~200 eligible patients or ~16 eligible patients/month; 100 total patients approached/16 eligible patients per month = 6.25 months.

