15.3 Statistical Analysis:

Data will be collected in REDCap and stored in an excel spreadsheet format in box and analyzed in-house with a statistician.

All analyses will be conducted using R or SAS statistical software. Values of $p < 0.05$ will be considered statistically significant. The analyses will use the intention-to-treat approach. The primary outcome will assume a complete case analysis, but when data is missing, methods for imputation will be explored based on the amount and type of missing data, potentially including multiple imputation using the mice package in R or linear interpolation methods for measures repeated over time that are missing for sensitivity analyses.

15.4 Data Integrity:

Data will be recorded automatically into the EPIC electronic health record system and will be extracted using computer algorithms/programs that have been tested for data extraction either by the research team or by the EPIC data team at Fairview. Any data extracted from the Vigilance II monitor with the VitalDB software package will be performed in real-time to a hospital-owned computer dedicated to the research team.

Data will be stored on hospital, password-protected computers via UMN Box. This will include laptops. Data will not be stored on personal computers of any kind,

MEDICAL PROTOCOL (HRP-590)

PROTOCOL TITLE: Comparison of normothermia maintenance between resistive blanket and forced air warming systems in renal transplant surgery

VERSION DATE: V43 January June 6, 2022

including smartphones. The computers will be stored in a locked office in the hospital, and only the research team will have access to these computers.

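### Section 18.2 allows an early stop for superiority at Z = 2.78, but Section 15.3 keeps the final test at p < 0.05 (overall error about 5.2%), and patient 55 is not halfway to 98

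*Combined protocol and SAP*

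**What the plan says.** Section 18.2 (Data Safety Monitoring) plans for the "DSMB to receive blinded (A vs B) data after the completion of the 55th patient (the halfway point"). It names an O'Brien-Fleming procedure and says the investigators "will stop the study if the SUPERIORITY of either method is established, based on an intergroup Z-score difference of 2.78". It gives no critical value or p-value for the final analysis and does not say which outcome the Z-score is computed on.

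Section 15.3 (Statistical Analysis) states: "Values of $p < 0.05$ will be considered statistically significant". It makes no exception for the primary outcome and does not mention the interim look. The same paragraph goes on to the primary analysis: "The primary outcome will assume a complete case analysis".

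Section 15.2 (Power Analysis) sizes the trial for a two-sided two-sample t-test at the full alpha of 0.05 and concludes: "We will take a conservative approach by enrolling 49 patients per group (98 patients total"). Section 10.2 repeats the total of 98. Section 5.2 identifies the primary outcome: "Our primary outcome variable is the NP temperature as recorded at the end of the surgery".

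**The concern.** A trial that can declare superiority at an interim look has two chances of a false positive. O'Brien-Fleming handles this with a pair of boundaries, a high one at the look and one slightly above 1.96 at the end. The protocol prints only the first. An analyst who follows Section 15.3 uses 1.96 at the end and exceeds the stated 5%.

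The missing value cannot be looked up without ambiguity, because it depends on the information fraction at the look. Section 18.2 gives two incompatible descriptions of that fraction: patient 55, and halfway. The unnamed outcome leaves another choice open. All of these should be settled before the monitoring board sees data by arm. Otherwise the final level could be chosen with the interim result in view.

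**Working it through.** **Inputs.** Difference 0.5°C, SD 0.75 (Section 10.2); two-sided alpha 0.05, 49 per group, 98 in total (Section 15.2); interim boundary 2.78 at patient 55 (Section 18.2); final threshold p < 0.05, that is |Z| > 1.96 (Section 15.3).

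**The plan's own sample size.** A two-sample t-test calculation at 90% power gives 48.26 per group, rounded up to 49, or 98 in total. This matches Section 15.2, as do the other seven rows of its table.

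**Timing.** 98/2 = 49, and 55/98 = 0.561. Patient 55 is not halfway to the other totals in the protocol either: 55/123 = 0.447 (patients to approach) and 55/130 = 0.423 (patients to consent). It is half of 110, which appears nowhere.

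**Overall type I error.** Under the null, the interim and final statistics Z1 and Z2 are bivariate normal with correlation √t, where t is the information fraction. The overall error is

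1 − P(|Z1| < 2.78 and |Z2| < 1.96).

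| Look | t | Overall error | Final critical value giving 5% | Final two-sided p |
|---|---|---|---|---|
| 49 of 98 | 0.500 | 5.21% | 1.979 | 0.0479 |
| 55 of 98 | 0.561 | 5.17% | 1.975 | 0.0483 |

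The last two columns solve 1 − P(|Z1| < 2.78 and |Z2| < c) = 0.05 for c.

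**Is 2.78 itself sound?** Yes. The classical two-look O'Brien-Fleming pair at t = 0.5 is 2.797 and 1.977. The Lan-DeMets O'Brien-Fleming-type pair at 55/98 is 2.774 and 1.975. The nominal two-sided p-value of Z = 2.78 is 0.0054.

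**With t-tests.** These are simulations of 1,000,000 null trials with 28 + 27 patients at the look and 49 + 49 at the end (Monte Carlo standard error about 0.0002):
- 2.78 applied directly to the t statistic, final p < 0.05: 5.28%.
- 2.78 converted to p = 0.0054, final p < 0.05: 5.18%.
- The same conversion with final p < 0.0483: 5.03%.

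With the look at 25 + 24, the first two become 5.35% and 5.23%.

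**What it means in degrees.** With 49 per group, the standard error is 0.75 × √(2/49) = 0.1515. On 96 degrees of freedom the smallest significant difference is 1.985 × 0.1515 = 0.301°C at p = 0.05, and 2.000 × 0.1515 = 0.303°C at p = 0.0483.

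**Power and chance of stopping.** The drift is 0.5/0.1515 = 3.300. With final |Z| > 1.96, overall power is 91.07% (look at 55) or 91.08% (look at 49). With the matched final value it is 90.83% or 90.78%. At patient 55 the expected Z is 3.300 × √0.561 = 2.472, so the chance of crossing 2.78 is P(Z > 0.308) = 37.9%. The t-test simulation, with the boundary as a p-value, gives 34.5%.

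**The case against.** Naming O'Brien-Fleming implies a paired final boundary, and a specific rule would normally govern a general sentence such as the one in Section 15.3. On that reading there is no inflation, only an unstated number. Sizing the trial at alpha 0.05 is not evidence against this, because an O'Brien-Fleming design also has an overall alpha of 0.05. This part of the objection has some force: the 5.2% belongs to the literal reading. But an implied value does not displace the only threshold that is printed, and the implied value differs according to whether the look is at 49 or 55.

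The effect is also very small. The excess is about 0.2 percentage points, and the window in which the conclusion changes is 0.002°C wide, against a meaningful difference of 0.5°C. That stands, and it limits the weight of the point. The miscount does not cause the excess either: a later look lowers it slightly.

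Finally, fixed levels of 0.0483 or 0.0479 are exact only if the look and the final number fall as planned, and a complete-case analysis may shift both. That is fair. It is a reason to state how the level follows from the actual numbers, not a reason to leave it unstated. The primary outcome is a natural default for the stopping rule, but a binding rule should name its outcome.

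**Conclusion.** The concern holds and should be fixed, although its numerical effect is small. As written, the final test at p < 0.05 after a superiority look at 2.78 gives an overall two-sided error of 5.17% (look at 55 of 98) or 5.21% (look at 49 of 98). If 2.78 is compared directly with a t statistic, it is about 5.3%. These figures assume a final total of 98, 1:1 allocation, a binding stop and a literal reading of Section 15.3. The interim boundary is acceptable. The gaps are the missing final level, the incorrect halfway statement and the unnamed outcome. The stopping rule is likely to matter in practice: under the planned effect, the trial has more than a one-in-three chance of ending at the look.

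**What to change.** **Section 18.2.**
- Either hold the look at patient 49, or keep patient 55 and describe it as 56% of 98.
- State that the rule applies to nasopharyngeal temperature at the end of surgery.
- Give the interim boundary as a nominal two-sided p-value of about 0.0054 (Z = 2.78), so that it carries over to a t-test.
- As an editorial correction, delete the reference to non-inferiority studies, since this is a superiority trial.

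**Section 15.3.**
- Set the final primary test at p < 0.0483 for a look at 55 of 98, or p < 0.0479 for a look at 49 of 98. Keep p < 0.05 for the other analyses.
- Add that, if the evaluable numbers differ from plan, the final level is solved from the actual information fraction in the same way.

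**Cost.** A few words in Section 18.2, a sentence or two in Section 15.3, and no extra patients. Power falls by 0.24 points with the look at 55 (91.07% to 90.83%) or 0.30 points at 49 (91.08% to 90.78%), and stays above the 90% target. The change should be made before the interim data are seen.

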4.3 Biosafety: N/A

4.4 Stem Cells: N/A

4.5 Fetal Tissue: N/A

5.0 Procedures Involved

5.1 Study Design:

Single institution, prospective, randomized, unblinded superiority study of renal transplant surgery participants, with no history of previous transplant, comparing a resistive blanket warming system (Hotdog (U102); Augustine Surgical, Inc., Eden Prairie, MN, USA) to a forced air warming system (Bair Hugger, Model 635; 3M Medical, St. Paul, MN, USA).

A randomization schedule will be developed using permuted block randomization with blocks of size 2, 4, 6, and 8 assuming 1:1 allocation within each block. Data will be analyzed using an intention-to-treat protocol.

5.2 Study Procedures:

The study will involve two arms: a resistive blanket warming system arm and a forced air warming system arm. Both devices will be set to warm the patient at each device's maximum setting at the beginning and throughout the case. The hotdog's maximum setting is 39C and the Bair Hugger's maximum setting is 41C.

The patient will be randomized to either the FAWS or RBWS before arrival to the operating room. Depending on which arm they have randomized to, the

MEDICAL PROTOCOL (HRP-590)

PROTOCOL TITLE: Comparison of normothermia maintenance between resistive blanket and forced air warming systems in renal transplant surgery

VERSION DATE: V43 January June 6, 2022

participant will be placed on either the underbody FAWS or the RBWS. An upper body FAWS will be placed on top of the patient prior to incision but is only to be utilized if normothermia cannot be achieved during the surgery with either device. The warming system that the patient is randomized to will be set up on the table before the participant is brought to the OR and transferred to the operating room table. The main warming device will be turned on once the patient is positioned on the operating table. The CRNA's will be involved in the placement of the blankets. Surgeons, OR Nurse Managers, and CRNA's will be informed by research team regarding patient's involvement in the study.

After the needed standard monitors for surgery have been placed, general anesthesia will be induced and maintained with patient's hemodynamics and other vitals maintained per standard care (no additional measurements beyond standard of care which is recorded in EPIC). Standard anesthetic care of the participant will occur for the duration of the surgery.

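### No estimate or interval allowing for an early stop is planned, although a stop at patient 55 tends to inflate the raw difference: at SD 0.75 and a true 0.5°C it averages about 0.70°C

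*Combined protocol and SAP*

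**What the plan says.** Section 18.2 (Data Safety Monitoring) has the monitoring board receive data once, "after the completion of the 55th patient (the halfway point"). It states that "we will use a well-established O'Brien-Fleming procedure" and that the investigators "will stop the study if the SUPERIORITY of either method is established, based on an intergroup Z-score difference of 2.78". The stop is written as a rule, and it works in either direction.

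Section 15.2 (Power Analysis) says "A mean difference of 0.5°C in patient temperatures between the two devices would be clinically meaningful". It adds that "limited data exists, so a range of standard deviations were explored", tabulating SDs of 0.25, 0.5, 0.75 and 1. The chosen size, 49 per group (98 in all), is the row for SD 0.75 and 90% power, and Section 10.2 gives the same SD.

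Sections 15.1 and 15.3 plan t-tests, regression for confounders, significance at p < 0.05 and methods for missing data. The only adjusted comparison is adjustment for confounders. Neither these sections nor 18.2 says how the difference or its interval would be reported after an interim stop.

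**The concern.** A trial that stops because its interim difference was large has selected that difference for being large. On average the raw estimate then lies further from zero than the truth, and an ordinary 95% interval ignores the selection. Here the selection happens near the difference the plan calls clinically meaningful. A reader of an early-stopped report will ask whether the gain reaches 0.5°C. A true effect well under 0.5°C could be reported as above it, with nothing in the analysis plan to warn the reader.

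**Working it through.** **Inputs.** Boundary |Z| = 2.78 at 55 patients (18.2). Allocation 1:1 (5.1), hence about 27 and 28 per arm. Difference 0.5°C with SD 0.75 (10.2, 15.2). Other SDs 0.25, 0.5 and 1 (15.2). Final size 98 (15.2). Assumption: Z is the difference in the primary outcome divided by its standard error, which 18.2 does not define.

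**The plan's own figure.** A two-sided two-sample t-test at 0.05 with a difference of 0.5°C, SD 0.75 and 90% power gives 49 per group. All eight rows of the 15.2 table reproduce.

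**Smallest difference that stops the study.** SE = SD × √(1/27 + 1/28) = 0.2697 × SD. The boundary is b = 2.78 × SE = 0.7498 × SD. At SD 0.75, SE = 0.2023 and b = 0.562°C. The boundary equals 0.5°C at SD = 0.5/0.7498 = 0.667, so a smaller observed SD allows a stop below 0.5°C.

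**Mean estimate at a stop.** For true difference δ, let a = (b − δ)/SE. Then P(stop) ≈ 1 − Φ(a), and the mean at a stop is δ + SE × φ(a)/(1 − Φ(a)). At SD 0.75 and δ = 0.5: a = 0.308, P(stop) = 0.379, mean = 0.5 + 0.2023 × 0.3804/0.379 = 0.703°C.

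| SD | Smallest difference at a stop | P(stop), true 0.5°C | Mean at a stop, true 0.5°C |
|---|---|---|---|
| 0.25 | 0.19°C | about 100% | 0.50°C |
| 0.5 | 0.37°C | 82% | 0.54°C |
| 0.75 | 0.56°C | 38% | 0.70°C |
| 1 | 0.75°C | 18% | 0.90°C |

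At SD 0.75, other true differences give 6% and 0.65°C (true 0.25°C), 82% and 0.81°C (true 0.75°C), and 98% and 1.01°C (true 1.0°C).

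**Bias over all trials (SD 0.75, true 0.5°C).** Trials that continue have interim mean (0.5 − 0.379 × 0.703)/0.621 = 0.376 and final mean (55 × 0.376 + 43 × 0.5)/98 = 0.430. Overall: 0.379 × 0.703 + 0.621 × 0.430 ≈ 0.534°C, a bias of about 0.03°C.

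**Coverage among stopped trials (SD 0.75).** For an interval of ± k × SE this is (Φ(k) − Φ(a))/(1 − Φ(a)), with k = 1.96 for the raw interval and 2.78 for the repeated interval.

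| True difference | Φ(a) | Raw 95% interval | Repeated interval |
|---|---|---|---|
| 0.25°C | 0.939 | 59% | about 95% |
| 0.4°C | 0.789 | 88% | about 99% |
| 0.5°C | 0.621 | 93% | about 99% |

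Over all trials, stopped or not, simulation gives raw coverage of 94.0%, 95.0% and 95.3% at true differences of 0.25, 0.5 and 0.75°C.

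**What the remedy gives.** For an observed 0.70°C at a stop (SD 0.75), the raw interval is 0.70 ± 1.96 × 0.2023, or 0.30 to 1.10°C. The repeated interval is 0.70 ± 0.562, or 0.14 to 1.26°C. The Whitehead estimate is the δ at which the expected estimate over the whole design equals 0.70. With final N = 98 it is 0.669°C. To check: at δ = 0.669, P(stop) = 0.701, the mean at a stop is 0.769 and the final mean of continuing trials is 0.537, so 0.701 × 0.769 + 0.299 × 0.537 ≈ 0.70.

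**SD estimated from the data.** Simulation with true SD 0.75 and a true 0.5°C gives 39% stopping and a mean of 0.69°C at a stop. About 2% of those stops show a difference below 0.5°C. With true SD 0.5, the share of stops below 0.5°C is about 39% (true 0.5°C) or 77% (true 0.3°C).

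**The case against.** The strongest case against acting is that little is at stake. Over all trials the bias at SD 0.75 is about 0.03°C and raw coverage is close to nominal. Where stopping is most likely, the inflation is small or absent (SD 0.25 and 0.5 in the first table). Coverage is poor mainly at a true 0.25°C, where a stop has only a 6% chance. The raw interval for an observed 0.70°C already includes 0.5°C; its lower limit passes 0.5°C only above 0.5 + 0.396 = 0.90°C. The documents also set no rule that a point estimate above 0.5°C establishes benefit. All of this stands, and it makes the point an improvement in reporting.

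It is also true that the bias-adjusted estimate does not settle the 0.5°C question. At the smallest stopping difference for SD 0.75 (0.562°C) it is still 0.527°C. The repeated interval has to carry that judgement.

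A reader might go further and infer that any early stop must show at least 0.56°C and so must clear 0.5°C. The documents do not support this. Z would use the observed SD, and Section 15.2 leaves the SD open from 0.25 to 1, so a stop below 0.5°C is possible whenever the observed SD is under about 0.667. Nor does every early stop overstate the effect: the inflation is an average, and it nearly vanishes when the true effect is large relative to the SD.

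What the objection does not remove is that the rule can stop the study with a chance of more than one in three under the design assumptions, and the plan says nothing about reporting in that case.

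**Conclusion.** The concern holds as a gap in reporting. At SD 0.75 and a true 0.5°C, the raw difference at a stop averages about 0.70°C, some 41% too high (0.703/0.5 = 1.41), and no planned estimate or interval allows for the stop. The clearest practical harm is a true effect below 0.5°C that stops early, where raw coverage among stops falls to about 59% (true 0.25°C) or 88% (true 0.4°C). Such stops are the less common ones, at about 6% and 21% of trials.

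The figures assume a 27/28 split (26/29 also gives 0.56°C), Z as difference over standard error, and a final size of 98. The adjusted estimate depends on that size: with 110 it would be 0.664°C in place of 0.669°C. Section 18.2 calls patient 55 the midpoint although half of 98 is 49; at 49 patients the smallest stopping difference at SD 0.75 would be 0.60°C. That mismatch is a separate matter, but it should be reconciled before the calculation is fixed.

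**What to change.** Add to Section 18.2, with a cross-reference in 15.3:

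> If the study stops at the interim analysis, the report will give, beside the raw mean difference, the repeated confidence interval (difference ± 2.78 × SE) and a bias-adjusted mean difference (Whitehead method, using the planned final sample size). Whether the 0.5°C difference is reached will be judged from the repeated interval and not from the raw interim estimate alone.

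The text should be settled before interim data are seen. It leaves the stopping rule and sample size as they are and needs a few lines of code.

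The downside arises only after an early stop: a wider, conservative interval (half-width 0.56 against 0.40°C at SD 0.75) and a slightly smaller estimate (0.70 to 0.67°C). At that SD the repeated interval would lie wholly above 0.5°C only if the observed difference exceeded 0.5 + 0.562 = 1.06°C, so many early stops would leave the 0.5°C question open. Nothing changes if the study runs to 98.
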